12.6.2. Treatment Period

✓ *Day 1 Dosing Visit*

The following procedures will be performed on subjects selected to proceed to the Treatment Period.

- Study drug accountability and dosing compliance: Study drug tube will be designated and a Dosing Diary will be provided to the subjects.
- Used and new study drug tubes will be weighed and the results recorded.
- Study drug application and completion of the Dosing Diary by the subject under the supervision of the site personnel.
- Subject instructions will be reviewed including appointment for the next visit. Study drug and study tools will be given to the subject.

✓ *Day 1 Post-Dose through Week 4 Visit*

- Subjects will dose at home and record each application in the Dosing Diary.
- Study drug application:
 - Subjects in Cohort 1 will apply study drug twice daily. On Day 1 subjects in Cohort 1 will apply the second dose at home in the evening.
 - Subjects in Cohort 2 will apply study drug once daily.
- Site personnel will communicate with the subjects approximately 2 weeks after Day 1 (Section 12.7) to review the trial instructions and Dosing Diary as well as to remind each subject of their next site visit. Subjects will be reminded to bring all study drug with them to the next visit.

✓ *Week 4 Visit*

On Day 29 (± 5 days) the following procedures will be performed:

- Adverse event(s) AEs will be recorded
- Concomitant medications documented
- Vital signs: peripheral blood pressure, respiratory and heart rates, and oral temperature will be recorded
- Physical examination
- Local Skin Reaction Score in the Treatment Field
- AK Lesions in the Treatment Field: count (Section 11.1.1)
- Study drug accountability and dosing compliance: Used study drug tube will be collected and new tubes designated. Dosing Diaries will be collected and reviewed with the subject, and a new diary will be provided to the subjects.
- Used and new study drug tubes will be weighed and the results recorded.

- Study drug application and completion of the Dosing Diary by the subject under the supervision of the site personnel.
- Trial instruction review including an appointment for the next visit will be given. Study drug and study tools (as required) will be re-supplied to the subject, as needed. Subjects will be reminded to bring all study drug with them to the next visit.

✓ ***Week 5 through Week 8 Visit***

- Subjects will dose at home and record each application in the Dosing Diary.
- Study drug application:
 - Subjects in Cohort 1 will apply study drug twice daily.
 - Subjects in Cohort 2 will apply study drug once daily.
- Site personnel will communicate with the subjects approximately 2 weeks after the Week 4 Visit (Section 12.7) to review the trial instructions and Dosing Diary as well as to remind each subject of their next site visit. Subjects will be reminded to bring all study drug with them to the next visit.

✓ ***Week 8 Visit***

On Day 57 (± 5 days) the following procedures will be performed:

- Adverse event(s) AEs will be recorded
- Concomitant medications documented
- Vital signs: peripheral blood pressure, respiratory and heart rates, and oral temperature will be recorded
- Physical examination
- Local Skin Reaction Score in the Treatment Field
- AK Lesions in the Treatment Field: count (Section 11.1.1)
- Study drug accountability and dosing compliance: Used study drug tube will be collected and new tubes designated. Dosing Diaries will be collected and reviewed with the subject, and a new diary will be provided to the subjects.
- Used and new study drug tubes will be weighed and the results recorded.
- Study drug application and completion of the Dosing Diary by the subject under the supervision of the site personnel.
- Trial instruction review including an appointment for the next visit will be given. Study drug and study tools (as required) will be re-supplied to the subject, as needed. Subjects will be reminded to bring all study drug with them to the next visit.

✓ ***Week 9 through Week 12 Visit***

- Subjects will dose at home and record each application in the Dosing Diary.

- Study drug application:
 - Subjects in Cohort 1 will apply study drug twice daily.
 - Subjects in Cohort 2 will apply study drug once daily.
- Site personnel will communicate with the subjects approximately 2 weeks after the Week 8 Visit (Section 12.7) to review the trial instructions and Dosing Diary as well as to remind each subject of their next site visit. Subjects will be reminded to bring all study drug with them to the next visit.

✓ ***Week 12 Visit***

On Day 85 (±5 days) the following procedures will be performed:

- Adverse event(s) AEs will be recorded
- Concomitant medications documented
- Vital signs: peripheral blood pressure, respiratory and heart rates, and oral temperature will be recorded
- Physical examination
- Local Skin Reaction Score in the Treatment Field
- AK Lesions in the Treatment Field: count (11.1.1)
- 12-lead ECG tracing recorded pre-dose. An original (duplicate) copy of each ECG is required. This ECG will also be transmitted to the central ECG laboratory
- Clinical laboratory tests including hematology, chemistry, coagulations, and urinalysis: Fasting status to be recorded
- Study drug accountability and dosing compliance: Used study drug tube will be collected. Dosing Diaries will be collected and reviewed with the subject. **Neither study drug nor Dosing Diaries will be returned to the subject.**
- Used study drug tubes will be weighed and the results recorded.
- Trial instructions will be reviewed including an appointment for the next visit will be given.

12.6.3. Post-Treatment Follow-Up Period

✓ ***Week 12 through Week 13 Visit***

- No procedures will be performed on these days.

✓ ***Week 13 Visit***

Note: *Despite the overlap between the windows for the Week 12 and Week 13 Visits, the Week 13 Visit should occur at least 5 days after the Week 12 Visit.*

On Day 92 (±5 days) the following procedures will be performed on all subjects:

- Adverse event(s) will be recorded

- Concomitant medications documented
- Urine Pregnancy Test will be performed on all women and results recorded.
- Local Skin Reaction Score in the Treatment Field
- AK lesion in the Treatment Field: count (11.1.1)
- Trial instruction review including an appointment for the next visit will be given.

✓ ***Week 14 through Week 16 Visit***

- Site personnel will communicate with the subjects on Week 15 (Section 12.7) to review the trial instructions and to remind each subject of their next site visit. Subjects will be reminded to bring all unreturned study drug with them to the next visit.

✓ ***Week 16 Visit***

On Day 113 (± 5) the following procedures will be performed on all subjects:

- Adverse event(s) will be recorded
- Concomitant medications documented
- Vital signs: peripheral blood pressure, respiratory and heart rates, and oral temperature will be recorded
- Physical examination
- Local Skin Reaction Score in the Treatment Field
- AK Lesion in the Treatment Field: count (11.1.1)

Subjects will be thanked for their participation in the trial and exit the study.

12.6.4. Early Termination Visit

Subjects exiting the study before completion of the Treatment Period should undergo Early Termination Visit assessments. The following assessments will be performed during such a visit.

- Adverse event(s) AEs will be recorded
- Concomitant medications documented
- Vital signs: peripheral blood pressure, respiratory and heart rates, and oral temperature will be recorded
- Physical examination
- Local Skin Reaction Score in the Treatment Field
- AK Lesions in the Treatment Field: count (11.1.1)
- 12-lead ECG tracing recorded pre-dose. An original (duplicate) copy of each ECG is required. This ECG will also be transmitted to the central ECG laboratory

- Clinical laboratory tests including hematology, chemistry, coagulations, and urinalysis: Fasting status to be recorded
- Study drug accountability and dosing compliance: study drug tubes will be weighed and the results recorded. Dosing Diaries will be collected. **Neither study drug nor Dosing Diaries will be returned to the subject.**
- Urine Pregnancy Testing will be performed on all women and results recorded.

12.7. Once-Monthly Subject Contact

Site personnel will contact each subject between study visits. These phone calls should be made, whenever possible, approximately 2 weeks after the Day 1, Week 4, Week 8, and Week 13 Visits. The goals of this contact are: (a) to review the dosing instructions and Dosing Diary with each subject; (b) to answer any questions raised by the study participants; (c) to remind subjects of their upcoming site visit and any related activities; (d) to remind subjects to bring their study drug to each site visit; and/or (e) to ask subjects not to take their dose on site visit days since the study drug dose on those days will be applied under the supervision of site personnel.

12.8. Unscheduled Visits

Investigators will invite subjects to attend an unscheduled visit to the investigative site (a) if during the trial a subject's medical condition warrants more frequent observations than prescribed by the clinical protocol and/or (b) if a subject has an AE that has not stabilized or resolved and requires additional visits or follow-up beyond the standard study days.

12.9. General Restrictions

12.9.1. Medication and Other Therapeutic Restrictions

Prohibited Products and Procedures

All prescription medications, vitamins, medicinal products, and AK therapies (including chemical peels and photodynamic therapy) are prohibited from Day 1 through the subject's exit from the study unless explicitly permitted below or approved in writing by the Investigator and Study Medical Monitor.

Topical creams, lotions, makeup, or gels of any kind are prohibited within the selected Treatment Field and the 3-inch area around the border of this field from Day 1 through the subject's exit from the study unless prescribed by the site Investigator and documented in the subject's file.

Permitted Products and Procedures

Allowed medications or therapies during the study must be documented and include:

- Daily medications: Subjects taking vitamins, prescription medications, or medical products daily may continue taking those products as long as the subject has been taking them continually for at least 2 months prior to Screening with no significant change in dose or dosing interval. These medicinal products must be recorded on the appropriate Concomitant Medication pages. All other prescription medications, medicinal products, and vitamins (with exceptions noted in the bullets below) are prohibited without prior approval of the Investigator and the Medical Monitor.
- Non-prescription prn medications: The following non-prescription medications are allowed without prior consultation: ≤ 1500 mg acetaminophen, ≤ 1650 mg naproxen, or ≤ 1200 mg ibuprofen within a 24-hour period for not more than 2 consecutive days.
- Prescription prn medications: Prescribed medications taken prn including antihistamines, bronchodilators, sleep medications, and intranasal, inhaled, and ophthalmic corticosteroids that are listed as concomitant medications at Screening and/or Day 1 Pre-Dose Visits are permitted. PRN medication taken daily are to be considered "daily medications."
- Physical treatments or procedures such as cryo-destruction, surgical excision, curettage, dermabrasion, or laser resurfacing more than 3 inches from the border of the Treatment Field are permitted.
- Topical creams, lotions, makeup, or gels applied outside the 3-inch border area of the selected Treatment Field is permissible. Subjects, however, should not change such products between and screening and their exit from the trial.
- Light bodied bland moisturizer (e.g., Cetaphil or Lubriderm without alpha-hydroxy acid) may be applied to the selected Treatment Field as an aid to managing AEs with the approval of the site Investigator. Moisturizers must not be applied within six hours of the last study drug application and the Treatment Field must be washed with soap prior to the next dosing.

12.9.2. Topical Non-Medicinal Product Restrictions

Subjects should be instructed not to change their cosmetics, soaps, shampoos, laundry detergents, deodorants, moisturizers, sunscreens, etc. from Day 1 through their exit from the trial.

12.9.3. Sun Protection and Tanning

Purposeful tanning and application of tanning agents are prohibited at any time during the trial. Subjects must avoid purposeful direct exposure to the sun or ultra-violet light from Day 1 through their trial exit. Subjects who go outdoors should wear proper clothing and hats that protect their skin from sunlight.

NOTE: Subjects should be encouraged to apply sunscreens that the subject has applied previously without untoward effects. Sunscreen products that have not been used previously by the subject must be avoided.

No topical sunscreens, creams, lotions, or gels of any kind may be applied within the selected Treatment Field or within the surrounding 3-inch border area from Day 1 through the subject's exit from the trial unless prescribed by the site Investigator and documented in the subject's file. Therefore, at Screening, subjects should be carefully instructed regarding this restriction as well as use of proper headwear to protect the Treatment Field and the surrounding skin.

12.9.4. Dietary Restrictions

Since this study does not include PK, subjects have no food restrictions.

12.9.5. Nicotine and Alcohol Restrictions

Subjects enrolled in the study have no smoking restrictions. Social drinking of alcoholic beverages is also not restricted.

12.9.6. Physical Exercise Restrictions

There are no restrictions placed upon physical exercise. However, subjects should not swim or perform strenuous activities within 6 hours after applying the study drug. If the subject would like to perform such activities, the study drug application should be postponed until after the activity has been completed.

12.10. Childbearing Potential

12.10.1. Definitions

Childbearing Potential: Female subjects with at least one of the following medical conditions will be considered lacking childbearing potential:

- a) aged \geq 50 years and last normal menstrual period was at least 12 months prior to Screening;

- b) undergone removal of her entire uterus (total hysterectomy); bilateral tubal ligation at least 6 months prior to Screening and/or bilateral oophorectomy

Females who do not meet at least 1 of the above criteria or do not have at least 1 criterion documented in the Medical History will be considered capable of childbearing and must be willing and able to use an acceptable form of contraception. Any subject meets this definition for childbearing and who cannot use an acceptable form of contraception, must be excluded from the study under Exclusion Criterion #3 (Section 9.2).

Acceptable forms of contraception are: a) hormonal contraceptives [e.g., oral, transdermal, injectable, or intravaginal], b) barrier methods [condom and spermicidal or diaphragm/cervical cap and spermicidal], c) partner vasectomy (performed at least six months prior to study entry), or d) total abstinence. Subjects who become sexually active or begin to have relations with a partner who is not sterile during the study must agree to use an effective form of birth control for the duration of the study.

Urine Pregnancy Test (UPT): All women enrolled in the trial must have a negative UPT at Screening and on Day 1 Pre-Dose before first study drug dosing. In addition, all women must also undergo a UPT testing approximately one week after the final study drug application.

12.10.2. Contraception

Women with childbearing potential (as defined in Section 12.10.1) must be able and willing to use a contraceptive method describes in that section, from Screening **until 1 month following the final study drug application.**

Non-vasectomized male subjects with female partners without childbearing potential (as defined in Section 12.10.1) are not required to use contraception.

Non-vasectomized male subjects with female partners with childbearing potential (as defined in Section 12.10.1) must agree to use an acceptable form of contraception (as defined in Section 12.10.1) from Screening until **3 months** after the last dose of study drug and must refrain from sperm donation for 3 months after the last dose of study drug.

Vasectomized males \geq 6 month post the vasectomy procedure, require no contraception.

13. STUDY MEDICATION

13.1. Description of Study Medication

The study drug will be manufactured, packaged, and labeled under GMP.

VDA-1102 is formulated as a milky-white ointment, with the drug substance being dissolved in a water-free ointment base.

- 10% VDA-1102 topical ointment is supplied in 15 grams (gm) aluminum tubes with plastic caps and stored refrigerated at 2-8 °C (36-46°F).
- 20% VDA-1102 is supplied in 10 grams (gm) aluminum tubes with plastic caps and stored refrigerated at 2-8 °C (36-46°F).

13.2. Drug Packaging

The study drug tubes are enclosed in an aluminum pouch with an enclosed desiccant. The pouch is packaged in a protective cardboard container.

13.3. Drug Labeling

Each tube will be labeled with the following information:

1. Study number
2. Name of the Sponsor
3. Drug name
4. Lot numbers
5. Directions for use
6. The statement, “Caution: New drug - limited by United States law to investigational use”
7. Storage conditions (degrees C and F)
8. Quantity

13.4. Study Drug Distribution

Study drug will be shipped under refrigerated conditions with temperature loggers from the drug depot to the site pharmacy.

13.5. Study Drug Storage

Site Pharmacy

All study drug will be stored at the investigative site or their institutional pharmacy at 2-8 °C (36-46°F) in a secured area with access limited by coded keypads and/or locks. The aluminum pouch and desiccant may be discarded once the pouch is opened at the site for the first study drug application.

Home Storage

Subjects will be instructed to keep the study drug tube in the accompanying cardboard container and to keep this unit in their home refrigerator.

Travel

If a subject must transport the study drug (for example, while travelling on vacation, on business, or to the site) they will be instructed to protect the study drug from heat in the supplied cooler pack. The drug should not be placed in the trunk of a car or in checked luggage on a plane.

Subjects planning to travel away from home should contact their site in order to receive instructions how to properly care for the study drug.

13.6. Study Drug Dispensing and Administration

13.6.1. Study Drug Dispensing

Following conclusion of the Day 1 Pre-Dose procedures, the Investigator (or designee) will assure that the subject still meets all the study enrollment criteria. The investigator may then approve subject enrolment.

Site personnel (or institutional pharmacist) will allocate the appropriate study drug for each subject. The tube with its aluminum envelope will be removed from the cardboard container in which it was stored while refrigerated. The aluminum envelope will be opened by site personnel and the tube removed. The aluminum envelope will be retained at the site for monitoring purposes and the tube will be returned to the container until dosing time.

Subjects will receive a new tube of the study drug at Day 1 Dosing, Week 4, and Week 8 Visits and tubes will be returned by the subjects at Week 4, Week 8, and Week 12 Visits.

13.6.2. Study Drug Dosing Cards

Study Drug Dosing Cards will be distributed to the site. These cards will be used: (a) by site personnel to train and to test subjects in the proper length of the study drug ointment strip to be expressed and applied to the Treatment Field, and (b) by enrolled subjects to measure the appropriate length of study drug ointment to be applied to their Treatment Field.

13.6.3. Study Drug Measurement and Application Review

All sites will receive tubes of placebo with which to train all subjects to measure the appropriate quantity of study drug to be applied. These training tubes will be clearly marked.

Using the Treatment Field photograph and Template, placebo training ointment, and a Study Drug Dosing Card, the subject will be trained and tested in proper and precise dosing techniques.

Note: Training tubes containing placebo ointment will only be used to practice measurement of the proper study drug dose on the Dosing Card and not for application to the face during training and testing.

Screening Visit

Subjects will be trained and tested by site personnel at the Screening Visit. The subject will be taught to measure the study drug using placebo tubes supplied by the Sponsor. The subjects will also be taught how to apply the study drug, but they will not use the placebo for this part of the training. In other words, placebo should not be applied to their skin during the training.

Subjects who have difficulty measuring the dose or applying the study drug to the precisely may be asked to bring a dosing partner with them to the Day 1 Pre-Dose Visit. This dosing partner must be willing and able to assist the subject with study drug application once every evening for 84 days.

If the subject (or their dosing partner) is unlikely to apply the study drug appropriately, the subject should be terminated from the study based on Inclusion #3 (Section 9.1).

Day 1 Pre-Dose Visit

Subjects who continue to meet the study enrollment criteria following Screening will be trained and tested twice by site personnel during the Day 1 Pre-Dose Visit: once at the beginning of the visit and once again at the end of the visit before randomization. If the subject (or dosing partner) is unlikely to apply the study drug appropriately, the subject should be excluded from the study based on Inclusion #3 (Section 9.1).

Day 1 Dosing Visit

Dosing at this visit will occur under the supervision of the site personnel. If at this visit the subject (or their dosing partner) is unable to precisely prepare the study drug or is unable to properly locate the Treatment Field, **they should be withdrawn before the study drug is applied and considered a screening failure.** Application of the study drug during this visit will be the same as described in Section 13.6.4, below.

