Study Design 
This Phase 2 clinical trial is a 3-part, open-label, multi-center study involving a non-occluded, daily topical dermal application of 1 of 2 strengths of VDA-1102 ointment for approximately 12 weeks (84 days) to an initial 2 cohorts of subjects. The first 40 eligible subjects will be enrolled into Cohort 1 (Part A). Cohort 1 subjects will be assigned to receive approximately 200 mg of 10% VDA-1102 twice-daily (BID). Once approximately 40 subjects have been enrolled in Cohort 1, Cohort 1 will be closed to enrollment and Cohort 2 (Part B) will be opened for enrollment. Cohort 2 subjects will be assigned to receive approximately 200 mg of 20% VDA-1102 once-daily (QD). Once approximately 40 subjects have been enrolled in Cohort 2, an additional 70 subjects will be randomly assigned to Cohort 1 or Cohort 2 (Part C) in a 1:1 ratio.
 
To qualify for the study, subjects aged 18 (inclusive) or older must have signed informed consent and met the study enrollment criteria that include having 4-8 actinic keratosis (AK) lesions within an approximate 25 cm² area on the cheek, forehead, or hairless scalp (the "Treatment Field").
	

Parts A, B, and C of this clinical trial will each include the same 3 study periods, a Screening Period (Day -21 through Day 1 Pre-Dose), a Treatment Period (Day 1 Dosing through Week 12), and a Post-Treatment Follow-Up Period (Week 13 through Week 16).

During the **Screening Visit** (up to 21 days pre-dose) subjects who have given written informed consent will undergo safety assessments, Treatment Field identification, and other qualifying procedures.

At the **Day 1 Pre-Dose Visit**, eligible subjects will return to the investigative site for baseline assessments as well as final eligibility screening. Subjects who continue to meet the enrollment criteria will be enrolled and will continue to the Day 1 Dosing Visit. The number of AK lesions within the Treatment Field will be recorded.

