7. STUDY DESIGN

7.1. Study Design: Study Weeks and Visits

This is a multi-center, open-label, 3-part, 2-cohort Phase 2b study involving daily non-occluded, topical dermal application of VDA-1102 ointment in subjects with actinic keratosis (AK). The study design is summarized in Figure 1.

To qualify for the study, male and female subjects aged 18 (inclusive) or older must have signed informed consent and have met the study enrollment criteria at the **Screening Visit** and Day 1 Pre-Dose Visit that include having 4-8 actinic keratosis (AK) lesion within an approximate 25 cm² area on the cheek, forehead or balding scalp (the “Treatment Field”).

Part A / Cohort 1

A total of approximately 75 subjects will be consecutively enrolled in Cohort 1. Enrolled subjects will apply approximately 200 mg of 10% VDA-1102 twice-daily to their Treatment Field for approximately 12 weeks. Safety assessments will occur on the **Day 1 Pre-Dose** and **Day 1 Dosing Visits**. Safety and efficacy assessments will be repeated at the **Week 4, 8 and 12 Visits**. This portion of the study will be called the **Treatment Period**.

Subjects will return for safety and efficacy assessments at the **Week 13 and 16 Visits (Post-Treatment Follow-Up Period)**.

Once approximately 40 subjects have been enrolled in Cohort 1, enrollment into this cohort will be closed and Cohort 2 will be opened to enrollment.

Part B / Cohort 2

Cohort 2 subjects will apply approximately 200 mg of 20% VDA-1102 to their Treatment Field each morning (QAM) for approximately 12 weeks.

The procedures and activities to be performed on subjects enrolled in Cohort 1 are the same as those to be performed on subjects in Cohort 2.

Part C / Cohorts 1 and 2

Once the number of subjects in Cohort 2 approximates the number in Cohort 1, Part C of the study will begin wherein approximately 70 eligible subjects will be randomly assigned to either Cohort 1 or Cohort 2. Thus, the trial will close with a total of approximately 75 subjects in each cohort.

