7.2.1. Screening Period (Day -21 through Day 1 Pre-Dose)

During the Screening Visit (up to approximately 21 days pre-dose) subjects who have given written informed consent will undergo screening, safety assessments, Treatment Field identification, and study drug application training.

At the Day 1 Pre-Dose Visit, eligible subjects will return to the investigative site for baseline assessments, final eligibility screening, Treatment Field identification, and study drug application training. AK lesions within the Treatment Field will be counted.

Three times during the Screening and Day 1 Pre-Dose Visits, subjects will be trained and tested in proper measurement and application of the study drug to the Treatment Field with the help of a Dosing Card and a flexible plastic stencil (“Treatment Field Template”). Subjects unable to apply the study drug properly will be excluded, unless they are accompanied by a dosing partner willing and able to properly dose the subject each day.

Subjects who continue to meet the enrollment criteria will be enrolled and will continue to the Day 1 Dosing Visit.

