13.6.4. Study Drug Administration at Home

The study drug will be applied to the Treatment Field by the subject or their dosing partner. Subjects in Cohort 1 will apply approximately 200 mg of 10%VDA-1102 each morning before 10:00 am and each evening at least 3 hours prior to bedtime. Subjects in Cohort 2 will apply approximately 200 mg of 20%VDA-1102 each morning before 10:00 am.

Cohorts 1 and 2: The morning dose should be applied before 10 am. **If a subject knows that they will perspire, shower, vigorously exercise, etc. before 10 am, application of the study drug should be delayed until completion of those activities.**

Cohort 1 only: The evening dose should be applied each day **at least 3 hours** before bedtime.

If the subject would like to shower, wash their face, shampoo their hair, etc., these should be performed prior to study drug application.

At the dosing time, the subject should check the Treatment Field in the mirror to assure it is clean and dry.

The study drug tube will be removed from the container, the tube cover unscrewed, and the study drug ointment expressed as a strip into the rectangle printed on the supplied Dosing Card.

Using a mirror, Treatment Field photograph, and/or the landmarks drawn on the Treatment Field Template, the template will be appropriately positioned on the subject's face or scalp. The subject (or dosing partner) will apply the study drug to the Treatment Field on their skin that corresponds to the 25 cm² area cut out of the template. Subjects (or their dosing partners) will apply the study drug with one finger to the center of the Treatment Field and spread the ointment evenly over the entire field. The Treatment Field will **not** be occluded. The subject will remove the Treatment Field Template from their face. With the same finger, the subject will spread ointment at the periphery of the Treatment Field approximately ¼ inch beyond the Treatment Field perimeter to ensure that the whole Treatment Field was covered with study drug.

After each study drug application, the subject's hands should be very carefully washed with warm water and soap.

The subject will be instructed not to wet or touch the Treatment Field. Subjects should not perform activities that might cause wetting or excessive sweating of the Treatment Field, for approximately 6 hours after dosing.

After each dosing, the Dosing Diary must be completed.

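### The dosing-partner condition in 13.6.3 (one application each evening) matches neither cohort's application schedule in 13.6.4

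*Combined protocol and SAP*

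**What the plan says.** Three parts of the protocol bear on this.

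- **Section 13.6.3, Screening Visit.** A subject who has trouble measuring or applying the drug may be asked to bring a partner to the Day 1 Pre-Dose Visit. The condition on that partner is to be "willing and able to assist the subject with study drug application once every evening for 84 days".
- **Section 13.6.4, home administration.** Cohort 1 applies drug "each morning before 10:00 am and each evening at least 3 hours prior to bedtime". For the other cohort, "Subjects in Cohort 2 will apply approximately 200 mg of 20%VDA-1102 each morning before 10:00 am". The evening instruction ("The evening dose should be applied each day") is marked as applying to Cohort 1 only. Section 7.1 agrees for Cohort 2 ("to their Treatment Field each morning (QAM) for approximately 12 weeks"), and section 7.2.2 and the list under Figure 1 also give that cohort's regimen as QAM.
- **Section 7.2.1, Screening Period.** Subjects who cannot apply the drug properly are excluded "unless they are accompanied by a dosing partner willing and able to properly dose the subject each day". No time of day or number of daily applications is given.

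**The concern.** For a subject who cannot apply the drug alone, having a suitable partner decides whether that subject can enrol, so the condition on the partner is an operative rule. Section 13.6.3 is the only place that states the partner's commitment by time of day and number of applications, and it describes a schedule that nobody in this trial follows.

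A site that takes the sentence at face value could ask a partner about evenings only and record the condition as met. If that partner turned out not to be available in the morning, a Cohort 1 subject who depends on the partner would lack help with one of two daily applications. A Cohort 2 subject would lack it for the only one. The result would be missed or mistimed applications in subjects who stay in the mITT summaries under their allocated cohort (17.7.2).

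In Part C the cohort is not yet known when the partner is assessed: 13.6.3 places the last training test at the end of the Day 1 Pre-Dose Visit, before randomization.

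**Working it through.** **Inputs**

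- Treatment duration: the synopsis gives it as "for approximately 12 weeks (84 days) to an initial 2 cohorts of subjects".
- Partner commitment (13.6.3): 1 application per day, in the evening, for 84 days.
- Cohort 1 (13.6.4): 2 applications per day, 1 morning and 1 evening.
- Cohort 2 (13.6.4, 7.1): 1 application per day, in the morning.
- Number of subjects who need a partner: not given.

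**Step 1. Reproduce the plan's figure.** 12 weeks × 7 days = 84 days. The duration in 13.6.3 is therefore consistent with the treatment period. Only the frequency and the time of day disagree.

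**Step 2. Count scheduled applications and match them to the commitment by time of day.**

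| | Morning | Evening | Total | Covered by one evening application per day | Not covered |
|---|---|---|---|---|---|
| Cohort 1 | 84 | 84 | 84 × 2 = 168 | 84 (84/168 = 50%) | 84 |
| Cohort 2 | 84 | 0 | 84 × 1 = 84 | 0 (0/84 = 0%) | 84 |

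The mismatch is partial for Cohort 1 and complete for Cohort 2. These are worst-case figures. They assume that the subject can apply nothing without help and that the partner is never available in the morning.

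**Step 3. How many subjects might be involved.** The documents do not say. Purely as an assumption, shares of 2%, 5%, 10% and 20% in a cohort of 75 would give 75 × 0.02 = 1.5, 75 × 0.05 = 3.75, 75 × 0.10 = 7.5 and 75 × 0.20 = 15 subjects. Nothing in the protocol favours one value over another, and an effect on clearance rates cannot be derived from them.

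**Step 4. Check whether other text supplies the missing schedule.**

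- 7.2.1 requires proper dosing each day, with no time or frequency.
- Exclusion Criterion 3 tests precision of application, not availability.
- 13.6.3 removes subjects whose partner is judged unlikely to apply the drug appropriately, but does not link that judgement to a schedule. It also cites Inclusion Criterion 3, which concerns lesion count; the criterion on application is Exclusion Criterion 3.
- The synopsis says that the subject or partner continues the prescribed regimen at home. That governs conduct after enrolment and does not say what the partner must agree to at qualification.

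None of these states a time or number of partner applications, so the contradiction remains.

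**Step 5. Possible origin.** Section 5.5.2 reports that the completed Phase 2 study used one application each evening. The sentence in 13.6.3 fits that study, with this trial's duration inserted. This is an inference and the point does not depend on it.

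**The case against.** The strongest reply is that a site reading the whole protocol would know when the partner has to act. The synopsis ties the partner to the prescribed regimen, 13.6.4 opens by naming the subject or partner and then sets out each cohort's schedule, and 13.6.3 twice lets the site turn away a subject whose partner is unlikely to do the job properly. This stands as mitigation. It does not correct a sentence that states a different commitment in mandatory terms.

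A reader might also infer more than the documents support:

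- **That such subjects cannot receive their regimen.** A commitment to evenings does not show that the partner is unavailable in the morning. The text also speaks of assisting a subject who has difficulty, so some subjects may manage part of the task alone. Sections 11.1.3 and 11.2 require lesions and Treatment Field to be easily visible to the subject in a mirror, which suggests that self-application is the usual case.
- **That Cohort 2 would lose all 84 applications.** The synopsis and rationale describe this cohort simply as once daily. Evening help could produce applications at an unscheduled time rather than missed ones.
- **That the comparison of regimens is compromised.** The synopsis plans no formal statistical analysis of efficacy, and 17.3.1 gives proportions with confidence intervals within each cohort.
- **That these subjects would drop out of the Per Protocol population.** The only example of a major deviation in 17.8 is more than 7 consecutive days of missed dosing. A Cohort 1 subject dosed every evening would not clearly meet it.

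Diaries, tube weights and calls between visits (13.7, 12.7) would also help to reveal missed applications. The problem of unknown allocation is confined to Part C, about 70 of 150 subjects; in Parts A and B only one cohort is open at a time.

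**Conclusion.** Wrong as written, and minor. The partner's commitment in 13.6.3 agrees with neither cohort's schedule in 13.6.4, and no other section supplies the time or number of applications to which a partner must agree. A site following 13.6.3 literally could therefore accept a partner whose stated commitment leaves scheduled applications uncovered. It does not follow that any site will do so.

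The coverage figures (50% in Cohort 1, none at the scheduled time in Cohort 2) are upper limits on the problem for one wholly dependent subject with a partner free only in the evening. They are not estimates for the trial. Without the number of partner-dependent subjects, no consequence for complete clearance, the mITT summaries or the Per Protocol set can be quantified, and none is claimed.

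**What to change.** Reconcile 13.6.3, 13.6.4 and 7.2.1 so that the partner's commitment and the cohort application schedules agree. The revision should take into account that in Part C the partner is assessed before the cohort is assigned. No schedule is proposed here; which text governs is for the sponsor to settle.

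The cost is one sentence in 13.6.3 and the matching site training material. A few partner-dependent subjects may no longer qualify. No change to the analysis or the sample size is needed.
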